 - a. Heart failure symptoms will be measured as the changes in KCCQ scores between the 30 day and 60 day time-points.
2. Patient daily log compliance.
 - a. Daily log compliance will be measured after 60 days using the total number of days patient completes daily log in the AMAZE™ app out of total days patient is enrolled in the app.
3. Patient app usage.
 - a. Patient app usage will be measured as the number of days the patient engages (i.e. completes daily log, sends a message) with the app at least once a day during the study period.
4. Patient app messaging.
 - a. Patient app messaging will be measured as the number of messages sent by the patient during the 60 day study period.
5. Changes in hospital readmissions.
 - a. Hospital readmission rates in the enrolled study group will be compared to readmission rates in historical control groups.
6. Use of ancillary healthcare resources.
 - a. Rates ancillary healthcare resources (i.e. emergency room visits, urgent care visits, unexpected ambulatory care visits, cardiac rehab) in the enrolled study group will be compared to rates of usage in a historical control group.

Subject Enrollment

Overview

Approximately 70 patients will be enrolled in the study. Patients admitted to MGH cardiology will be screened by study staff for inclusion/exclusion criteria. Study staff will obtain approval to approach eligible patients by the inpatient clinical team. Approximately 2-days prior to discharge, suitable patients will be consented and onboarded with study staff, with the technical support available 24/7 via email or phone through BrightInsight, Inc.

Procedure for obtaining informed consent

We will use Mass General Brigham electronic resources to identify and screen patients for the eligibility criteria listed above. Our internal (MGH) data and analytics team developed an automated process to screen and extract a list of eligible admitted patients on Ellison 10/11 through Research Patient Data Registry (RDPR) and Enterprise Data Warehouse (EDW) (IRB Protocol # 2020P002432). The list will be sent to the study staff daily; study staff will perform chart review of participants on the list to confirm eligibility.

We will focus on patients with a diagnosis of heart failure, who speak and read English.

We will also use the attached study flyer to advertise the study to patients on inpatient floors, with nurse manager approval for the respective floors.

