Research coordinators will conduct the two rounds of interviews at the 30- and 60-day follow-up calls respectively and record responses in REDCap. We will select four participants who are engaged with the app and one who is not to interview at their 30-day follow-up call. These same five participants will be interviewed at their 60-day follow-up call. A separate group of five participants, four who are engaged with the app and one who is not, will be interviewed only at their 60-day follow-up call.

[figure not shown]
Study Closeout and Post Study Follow-up

Ongoing participation is voluntary; patients can stop using the app at any time and withdraw from the study with no associated risk. Study staff will not withdraw participants from the study based on a lack of engagement with the app. When participants withdraw or complete the study, the nurse will send patients an off-boarding summary with the most current clinical recommendations from their care team, symptom reporting tips and most current prescribed medications. We will send the off-boarding summary to patients via Patient Gateway or email.

A separate message will be sent to the cardiology care team to notify them of the participant's status change in the study. Subjects will be reminded during the 60-day phone call that they should delete the AMAZE app. For participants who do not delete the application, the ability to use the app will end once it is deactivated via BrightInsight, Inc. due to withdrawal or completion of the pilot study.

Clinician Surveying

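### Daily log compliance (exploratory outcome 2a) is compliance while enrolled: it is at or above 60-day compliance of all enrolled patients, by an amount set by an unstated withdrawal rate

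*Combined protocol and SAP*

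**What the plan says.** Section III, Study Outcomes, exploratory item 2a, gives the numerator: "Daily log compliance will be measured after 60 days using the total number of days patient completes daily log". The denominator is "out of total days patient is enrolled in the app". The protocol does not define when app enrolment starts or ends, or how patient values are combined into a group figure.

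Section III, Study Closeout and Post Study Follow-up, bears on when enrolment ends. It says that "patients can stop using the app at any time and withdraw from the study", and that for those who keep the app installed "the ability to use the app will end once it is deactivated via BrightInsight, Inc. due to withdrawal or completion of the pilot study". It also says: "Study staff will not withdraw participants from the study based on a lack of engagement with the app". No expected withdrawal rate is given anywhere.

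The two neighbouring engagement outcomes do not use enrolled days. Item 3 counts days with any engagement, either a log or a message, over the study period. Item 4 is the "number of messages sent by the patient during the 60 day study period". On sample size: "Approximately 70 patients will be enrolled in the study".

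**The concern.** The denominator varies by patient, and what shortens it is formal withdrawal rather than stopping use of the app. A patient who stops logging and withdraws is scored only on the days before leaving. A patient who stops on the same day but says nothing is scored over the whole period, because staff do not withdraw patients for non-engagement. Identical log records can therefore give very different values.

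What is at stake is how the figure is read. Section II presents the pilot as a step towards a larger efficacy study, and Section V hopes it will guide later work on app use. A reader planning such work may take the compliance figure as the share of 60 days on which an enrolled patient logs. The ratio as defined answers a narrower question: how often patients log while they remain enrolled.

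**Working it through.** **Stated figure.** The protocol gives no target, expected value or precision for daily log compliance, so there is nothing to reproduce. The only power statement (Section VI) concerns the KCCQ and does not bear on this point.

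**Inputs from the protocol.** About 70 patients; 60 days of follow-up; denominator equal to days enrolled; withdrawal allowed at any time.

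**Assumptions.** App enrolment ends at withdrawal or at day 60. Deaths are ignored. Withdrawal rates, timing and logging rates are illustrative.

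**One patient.** Let L be days logged and E days enrolled, with E no more than 60.

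- Ratio as defined: L/E
- 60-day version: L/60
- Difference: L/E − L/60 = (L/E)(1 − E/60)

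The difference is never negative. It is positive exactly when L is at least 1 and E is below 60.

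Example: two patients each log 12 of the first 15 days and then stop. The one who withdraws at day 15 scores 12/15 = 80%. The one who stays enrolled scores 12/60 = 20%. On a 60-day denominator both score 20%.

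**Group.** Let a share q withdraw at day t, having logged on a fraction c of days until then. Averaging per-patient values, the gap between the two versions is q × c × (1 − t/60). The logging rate of those who stay cancels.

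If everyone logs 80% while enrolled and leavers go at day 15, the defined ratio is 80% whatever q is. The 60-day mean is (1 − q) × 0.80 + q × 0.80 × 15/60:

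- q = 10%: 74%
- q = 20%: 68%
- q = 30%: 62%

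That case is unfavourable to the defined ratio, because leavers are assumed to log as well as stayers. The table instead fixes stayers at 70% with N = 70 and varies the leavers. Mean is the average of per-patient ratios; pooled is total logs over total enrolled days.

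| Withdraw (n) | Day | Leavers' logging | As defined, mean | As defined, pooled | 60-day | Gap, mean | Gap, pooled |
|---|---|---|---|---|---|---|---|
| 0 | – | – | 70.0% | 70.0% | 70.0% | 0 | 0 |
| 5% (4, rounded) | 30 | 20% | 67.1% | 68.5% | 66.6% | 0.6 | 2.0 |
| 10% (7) | 30 | 40% | 67.0% | 68.4% | 65.0% | 2.0 | 3.4 |
| 20% (14) | 30 | 40% | 64.0% | 66.7% | 60.0% | 4.0 | 6.7 |
| 20% (14) | 15 | 70% | 70.0% | 70.0% | 59.5% | 10.5 | 10.5 |
| 30% (21) | 15 | 70% | 70.0% | 70.0% | 54.25% | 15.75 | 15.75 |

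Third row in full: logs = 63 × 60 × 0.70 + 7 × 30 × 0.40 = 2,646 + 84 = 2,730.

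- 60-day: 2,730/4,200 = 65.0%
- Pooled: 2,730/(3,780 + 210) = 68.4%
- Mean: (63 × 0.70 + 7 × 0.40)/70 = 67.0%

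The first two non-zero rows also show that the unstated choice between mean and pooled moves the defined figure by 1.4 points.

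**The case against.** Compliance while enrolled is a legitimate quantity, and it is what item 2a says it measures. It is too high only against a 60-day target that the protocol does not set. App access ends at deactivation, so a 60-day denominator counts days on which logging was impossible. This stands as a reason to keep the defined ratio and label it. It does not make the ratio a measure of 60-day logging across all enrolled patients.

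A reader might infer that withdrawn patients vanish from the calculation. They do not: only their days after withdrawal leave the denominator, and their earlier days and logs still count. A reader might also infer that the reported figure is bound to be inflated. That requires early withdrawal by patients who have logged, and no rate is given. The rule against withdrawing disengaged patients confines the effect to those who leave formally.

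Nor does the plan hide drop-off altogether. Item 3 counts engaged days over the study period without dividing by enrolled days, so it partly shows the loss. It counts messages as well as logs, though, and so does not replace item 2a.

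Finally, feasibility is defined by conversion rate and perceived value by the MAUQ. Log compliance is exploratory with no threshold, and the protocol does not say that the figure will enter a later design. All of this stands, and it limits the importance of the point.

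**Conclusion.** The point holds as a matter of definition and labelling. Item 2a gives compliance while enrolled, which equals or exceeds 60-day compliance of all enrolled patients. It is strictly higher whenever a patient with at least one log withdraws early. The direction follows from algebra, provided that enrolled days stop at withdrawal and do not run past 60. The first condition is the natural reading of the closeout section but is not stated outright.

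The size is unknown. It is zero without early withdrawals. With per-patient averaging it is about 0.6 to 16 points for assumed withdrawal of 5 to 30% at day 15 or 30 and prior logging of 20 to 70%. The documents do not support a claim that feasibility would be wrongly concluded: no primary outcome, threshold or sample size depends on this ratio. The change is worth making because it is cheap and frees the engagement estimate from whether a departure was formal.

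**What to change.** Amend item 2a to report two figures:

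- **60-day log compliance:** days with a completed log divided by 60 days from app onboarding, for every enrolled patient. Days after withdrawal count as not logged, and follow-up is truncated at death.
- **Compliance while enrolled:** the existing ratio, labelled as such, with app enrolment stated to run from onboarding to withdrawal, death or day 60.

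Average per-patient values in both versions, and report the number and timing of withdrawals beside them. State also how days in hospital on readmission are counted, since the protocol is silent on this.

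The cost is a few sentences in the outcome definition. The data needed are the app logs and the onboarding, withdrawal and death dates. The downside is that the 60-day figure will look somewhat less favourable if patients leave early.

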The clinician dashboard is also produced by BrightInsight, Inc to work in conjunction with the DMP App for patients. AstraZeneca aims to strengthen existing clinical resources and reduce the burden and time spent on patient preparation and follow-ups by surfacing real-time insights to clinical teams and providing the tools to support patients easily and efficiently. The dashboard features secure, 2-way messaging to individuals and groups of patients, enabling efficient follow-up to answer patients’ questions and outreach to encourage engagement with the disease management platform. Clinicians can also reach out to patients through multi-channel communication methods, including email linked to Patient Gateway and a text chat feature in the App, to promote engagement and responses to surveys. The clinical team is alerted based on patients’ survey responses and engagement patterns, allowing them to identify risks, intervene early through supportive messaging, and reduce post-admission recovery complications. In summary the goals here is to provide, the real-time information about patients’ health status, combined with secure easy messaging with patients, which will enable an efficient, effective workflow for clinical teams to support patients through recovery and health maintenance.

III. RESEARCH DESIGN AND METHODS

Sample size: 70 post hospital admission at Massachusetts General Hospital (MGH), general cardiology with a diagnosis of heart failure with reduced ejection fraction (HFrEF), heart failure with moderate ejection fraction (HFmEF), or heart failure with preserved ejection fraction (HFpEF). Patients will be identified via an automated computer-based algorithm using information retrieved from electronic health records {Protocol #: 2020P002432}.

Inclusion/Exclusion Criteria for intervention study population

- **Intervention study population:** Patients 21 years and older with a diagnosis of heart failure [HFrEF(<40%), HFmEF(40-49%) HFpEF(≥50%)] admitted to MGH cardiology services (Ellison 10 and 11). Patients must have access to smartphone and email, be English speaking/reading and discharged home.

Non-recruited EHR-based control populations for the exploratory objectives for this single-arm interventional pilot:

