- **Historical MGH control population:** Patients 21 years and older with a diagnosis of HF admitted to MGH cardiology services (Ellison 10 and 11) admitted in the year prior discharged home. Matched 1:2 based on age, sex, HFrEF(<40%), HFmEF(40-49%) HFpEF(≥50%), CAD, T2D, month admitted (minus 1y), number of prior 12mo hospital admissions.
- **Contemporaneous BWH control population:** Patients 21 years and older with a diagnosis of HF admitted to BWH cardiology services admitted during intervention study population enrollment and discharged home. Matched 1:2 based on age, sex, HFrEF(<40%), HFmEF(40-49%) HFpEF(≥50%), CAD, T2D, month admitted, number of prior 12mo hospital admissions.
- **Historical BWH control population:** Patients 21 years and older with a diagnosis of HF admitted to BWH cardiology services admitted in the year prior discharged home. Matched 1:2 based on age, sex, HFrEF(<40%), HFmEF(40-49%) HFpEF(≥50%), CAD, T2D, month admitted (minus 1y), number of prior 12mo hospital admissions.

Inclusion Criteria

- Adults (>21 years) admitted to MGH Cardiology services (Ellison 10 and 11) with a diagnosis of acute or chronic heart failure [HFrEF(<40%), HFmEF(40-49%) HFpEF(≥50%)] (or to BWH Cardiology services for BWH EHR-based controls)
- Has a smartphone or iPad and is willing to enter health metrics into DMP App and email willing to use for the study
- Access to the internet
- Established or with plan to establish primary cardiologist at MGH (or at BWH for BWH EHR-based controls)
- Discharged home or to self-care (with or without home services)

Exclusion Criteria

- Moderate or severe cognitive impairment
- Non-English-speaking
- Palliative management only (comfort measures)
- Does not own a smartphone or iPad (not considered for EHR-based controls)
- Incarcerated
- Enrolled in study with similar outcomes

Study Outcomes

Primary: To test the feasibility of implementing the AMAZE™ disease management platform intervention after in-patient heart failure hospitalization and patient perceived value of the AMAZE™ disease management platform. The feasibility will be measured using conversion rate (percent of patients approached who enroll on the disease management platform). The perceived value will be measured using the participants mHealth App Usability Questionnaire (MAUQ) score.

Exploratory: The following exploratory outcomes will be measured as follows:

1. Heart failure symptom changes using the Kansas City Cardiomyopathy Questionnaire (KCCQ).

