Patients will be surveyed for baseline demographics and study outcomes. Medical history, including labs, procedures, and diagnoses will be collected from the medical record and recorded in REDCap

At consent, subjects will be surveyed for demographics that cannot be obtained from the medical record (See “Baseline Demographics” attachment).

Quality of life will be collected through the patient-facing AMAZE app (See “KCCQ” attachment). Patient satisfaction will be collected through MAUQ (attached) administered through the app. The app will also track patient medication adherence, and facilitate symptom, blood pressure, weight, and activity tracking.

At roughly 30 days from enrollment and again at 60 days from enrollment, a research coordinator will call the patient to collect 1) current cardiac medications and any changes to medication regimen and 2) hospitalizations, ED presentations, urgent care visits, primary care or cardiology visits, and cardiac rehab enrollment at institutions outside MGB. Research coordinators will review subject medical records to determine these events at MGB.

EHR data for the control populations (MGH and BWH) will be obtained from RPDR. We may also review medical records for these patients to collect/confirm EHR data.

Optional interviews

Two rounds of interviews regarding the user experience of the AMAZE app may be conducted over the course of the study. The interview questions ask about usability and helpfulness of the app, along with the option to give feedback about technical issues and features that could use improvement. These interviews

are optional and do not affect the participants' overall participation in the study. This is reflected in the consent form, with a section allocated to participants' choice of whether they would like to be contacted for these interviews or not.

Participants who consent to being contacted for the interviews will be selected based on engagement with the app. We will measure engagement by percentage of daily log compliance over the past seven days. Participants who fill out the daily log more than half the days in a week will be classified as "engaged with the app" and those who fill out the daily log less than half the days in a week will be categorized as "disengaged with the app."

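### Exploratory outcomes 5a and 6a name only historical comparators, so as written the platform cannot be separated from calendar year

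*Combined protocol and SAP*

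**What the plan says.** Section III introduces the controls as "Non-recruited EHR-based control populations for the exploratory objectives for this single-arm interventional pilot". Three sets follow, each matched 1:2:

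- **Historical MGH:** patients "admitted to MGH cardiology services (Ellison 10 and 11) admitted in the year prior discharged home".
- **Contemporaneous BWH:** patients "admitted to BWH cardiology services admitted during intervention study population enrollment and discharged home".
- **Historical BWH:** the same hospital as the second set, one year earlier.

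The historical sets are matched on admission month shifted back one year, and the contemporaneous set on the same month.

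Under Study Outcomes, only exploratory outcomes 5 and 6 use controls. Outcome 5a reads "Hospital readmission rates in the enrolled study group will be compared to readmission rates in historical control groups". Outcome 6a says that ancillary resource use "in the enrolled study group will be compared to rates of usage in a historical control group", in the singular and without identifying the group.

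The remaining text on controls deals with obtaining, storing and sharing their data. Section VI (Power Analysis) concerns the KCCQ only.

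**The concern.** The section that defines the controls separates historical from contemporaneous sets, yet the outcome definitions call for historical ones only. Matching on month less one year aligns season but fixes a one-year gap between every participant and every comparator. A difference in readmissions or ancillary care could then come from the platform or from the year; against historical BWH it could also come from the hospital. Section II describes the pandemic as current and as a strain on contact between clinicians and patients, so the documents give no ground for assuming a stable year.

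The stakes are limited. The outcomes are exploratory and have no success criterion, and conversion rate and MAUQ use no controls. Section II calls the pilot a step towards a large efficacy study, but nothing says that 5a or 6a will size or justify that study.

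**Working it through.** The plan states no rate, trend, test or precision for outcomes 5 and 6, so there is no figure of its own to reproduce.

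**1. What can be estimated**

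Let *a* be the BWH mean in the prior year, *s* the hospital difference (MGH minus BWH), *y* the change from prior to current year and *t* the platform effect.

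| Group | Expected value |
|---|---|
| Enrolled MGH | a + s + y + t |
| Historical MGH | a + s |
| Historical BWH | a |
| Contemporaneous BWH | a + y |

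- Enrolled minus historical MGH = y + t.
- Enrolled minus historical BWH = s + y + t.
- Enrolled minus contemporaneous BWH = s + t.
- (Enrolled − historical MGH) − (contemporaneous BWH − historical BWH) = t.

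With the first three groups only, *y* and *t* always occur together: the design has rank 3 for 4 parameters. The contemporaneous BWH group raises the rank to 4 and makes *t* estimable, provided *y* is the same at both hospitals. If the hospitals' yearly changes differ by *g*, the last contrast equals t + g. None of this depends on the event rate.

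**2. Precision (illustrative)**

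From the documents: 70 enrolled and 1:2 matching, hence 140 per set. Assumed: event rate p of 20% to 30%, no platform effect, matched patients treated as independent. With v = p(1 − p):

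- SE of the MGH prior-year contrast = √(v/70 + v/140)
- SE of the difference-in-differences = √(v/70 + 3v/140)
- Ratio = √(5/3) = 1.291, so 29% larger.

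At p = 0.25, v = 0.1875. The SEs are √(0.1875 × 3/140) = 6.34 points and √(0.1875 × 5/140) = 8.18 points. The 95% half-widths are 1.96 × 6.34 = 12.4 and 1.96 × 8.18 = 16.0 points.

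**3. Bias against precision**

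A yearly shift *b* enters the prior-year contrast in full, so its root mean squared error (RMSE) is √(SE² + b²). Under a shared trend, the RMSE of the difference-in-differences equals its SE. Break-even is at b = √(v/70).

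| p | Prior-year SE | Prior-year RMSE, b = 5 | Prior-year RMSE, b = 10 | Difference-in-differences RMSE | Break-even b |
|---|---|---|---|---|---|
| 0.20 | 5.86 | 7.70 | 11.59 | 7.56 | 4.78 |
| 0.25 | 6.34 | 8.07 | 11.84 | 8.18 | 5.18 |
| 0.30 | 6.71 | 8.37 | 12.04 | 8.66 | 5.48 |

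All entries except p are in percentage points. Using each year's own variance and shifts in either direction, break-even runs from 4.6 to 5.6 points.

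**4. If the trends are not shared**

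At p = 0.25, a trend gap *g* of 3 points gives a difference-in-differences RMSE of √(8.18² + 3²) = 8.7 and break-even at √(5.18² + 3²) = 6.0 points. With g = 5, these become 9.6 and 7.2.

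**The case against.** - **Loose wording.** The introductory sentence ties all three sets to the exploratory objectives, and only outcomes 5 and 6 can use them. The contemporaneous set was evidently meant to be used, and "historical" may simply have stood for all record-based controls. This is plausible, and it means the data for a better comparison are already planned. But the protocol itself distinguishes the two terms, and even on the generous reading no contrast is named and 6a's single group is unidentified. The study schematic could not be read in the text available, so the finding covers the written text only.
- **The alternative is noisier and rests on its own assumption.** This stands. With no yearly shift the difference-in-differences is clearly less precise, and at 5 points it is no better. The break-even near 5 points assumes a shared trend, which the documents do not support. If 5a's plural means pooling both historical sets (280 controls), the simple contrast's SE at 25% is √(0.1875 × (1/70 + 1/280)) = 5.8 points, and the difference-in-differences SE is 41% larger. These are reasons to report it beside the simple contrasts, not instead of them.
- **Exploratory only.** This is true and limits how serious the point is. It does not make a confounded estimate interpretable.

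**Conclusion.** The concern holds. Read as written, 5a and 6a confound the platform with calendar year, and that conclusion needs no numerical assumption. The size of any resulting bias is unknown: it equals the yearly shift, for which the documents give no figure. Under the illustrative inputs (25% rate, independence, no platform effect, shared trend), a 10-point shift gives an RMSE of 11.8 points for the prior-year contrast against 8.2 for the difference-in-differences, while a 5-point shift leaves them about equal. The text should be corrected, but the effect is confined to the interpretation of two exploratory outcomes.

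**What to change.** Reconcile the control definitions with 5a and 6a by naming all three sets for both outcomes. Report these as exploratory estimates with 95% confidence intervals that respect the matched sets, without tests:

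1. MGH enrolled minus MGH historical.
2. MGH enrolled minus BWH contemporaneous, which replaces the year difference with a hospital difference.
3. The difference-in-differences: contrast 1 minus (BWH contemporaneous minus BWH historical).

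State that contrast 3 addresses calendar time only if the two hospitals share a trend, and that selection on smartphone ownership and consent remains in all three.

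A secondary point concerns Data Collection and Surveys. Participants are telephoned about events outside MGB, and for events inside it "Research coordinators will review subject medical records to determine these events at MGB". For controls, "EHR data for the control populations (MGH and BWH) will be obtained from RPDR", with chart review only optional: "We may also review medical records for these patients to collect/confirm EHR data". More events can therefore be found in participants. Add a sensitivity comparison limited to MGB events taken from the same source in all four groups.

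**Cost.** The main change is wording plus analysis of control data already planned, with no new patients. Contrast 3 has an interval about 29% wider than contrast 1 (half-width 16.0 against 12.4 points at the assumed 25%). The sensitivity comparison needs an RPDR extract of events for about 70 participants, or else chart review of up to 3 × 140 = 420 controls, and it discards participants' outside events.

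### Exploratory outcome 6a: resource use is not counted on the same basis in enrolled patients and controls, and unexpected visits have no common definition

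*Combined protocol and SAP*

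**What the plan says.** Under Study Outcomes, exploratory outcome 6 is the use of ancillary healthcare resources. Item 6a lists "emergency room visits, urgent care visits, unexpected ambulatory care visits, cardiac rehab" and says that these rates "in the enrolled study group will be compared to rates of usage in a historical control group". It does not define *unexpected*, name a direction of benefit, or say whether the components are summed or shown one by one.

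Data Collection and Surveys describes three sources:

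- **Enrolled patients, outside MGB.** "At roughly 30 days from enrollment and again at 60 days from enrollment, a research coordinator will call the patient", and among the items collected are "hospitalizations, ED presentations, urgent care visits, primary care or cardiology visits, and cardiac rehab enrollment at institutions outside MGB".
- **Enrolled patients, at MGB.** "Research coordinators will review subject medical records to determine these events at MGB".
- **Controls.** "EHR data for the control populations (MGH and BWH) will be obtained from RPDR", followed by "We may also review medical records for these patients to collect/confirm EHR data".

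**The concern.** The outcome asks for something that the described data collection does not record as such. An unexpected visit is a subset of ambulatory visits, and the listed call topics cover all primary care and cardiology visits. Patients leaving hospital with heart failure have planned follow-up: the inclusion criteria require an established or intended primary cardiologist, and Expected Benefits refers to a heart failure follow-up appointment after discharge. If planned visits enter the count, they dilute any difference in unexpected ones.

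The second problem affects every component. Events outside MGB are sought by telephone from enrolled patients, and no matching source is described for controls. Enrolled patients can therefore appear to use more care simply because they were asked.

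At stake is how a resource-use signal from this pilot would be read when the larger study is planned. The primary outcomes are not at stake.

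**Working it through.** The documents state no rate, effect size or test for outcome 6, and the Power Analysis section concerns the KCCQ only. There is no planned figure to reproduce. The check sets the sections side by side and then illustrates the two distortions with assumed rates.

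**Step 1. What 6a needs against what is described.**

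| Component in 6a | Enrolled, outside MGB (calls) | Enrolled, at MGB (chart review) | Controls (RPDR, chart review optional) |
|---|---|---|---|
| Emergency room visits | Collected | Collected | MGB records; no outside source described |
| Urgent care visits | Collected | Collected | Same |
| Unexpected ambulatory visits | All primary care or cardiology visits; no planned/unexpected attribute stated | Same visit types; no classification rule | No classification rule; no outside source described |
| Cardiac rehab | Enrollment | Enrollment | MGB records; no outside source described |

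Only the ambulatory row lacks a definition. All four rows have unequal sources. The outcome also speaks of rehab usage where the calls record enrollment.

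**Step 2. Dilution by planned visits.** Let *u* be unexpected visits per patient and *p* planned visits per patient, with *p* equal in both groups. If all visits are counted, the ratio is (*u* enrolled + *p*) / (*u* control + *p*). Assume *u* = 0.20 enrolled and 0.30 control:

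- *p* = 0: 0.20/0.30 = 0.67
- *p* = 1: 1.20/1.30 = 0.92
- *p* = 2: 2.20/2.30 = 0.96
- *p* = 3: 3.20/3.30 = 0.97

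A one-third reduction would appear as 3% to 8%. If planned visits differ between the groups, the error can go either way.

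**Step 3. Outside care counted in one group only.** Let *f* be the share of visits made outside MGB, equal in both groups. Suppose the calls capture all of these for enrolled patients and nothing captures them for controls. Then observed ratio = true ratio / (1 − *f*), which exceeds the true ratio whenever *f* > 0. The documents give no value for *f*. Assume acute visits of 0.30 enrolled and 0.40 control, a true ratio of 0.75. The observed ratio runs from 0.75 at *f* = 0 to 0.75/(1 − 0.25) = 1.00 at *f* = 0.25, and goes above 1 beyond that. At *f* = 0.25 only 0.40 × 0.75 = 0.30 control visits are seen, against 0.30 in the enrolled group, so the difference disappears.

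**Step 4. What is unaffected.** Emergency visits, urgent care visits and rehab enrollment are listed as distinct items, so the dilution in Step 2 does not reach them. The unequal capture in Step 3 does.

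**The case against.** The plan can be defended on several grounds.

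- The call form itself is not in the documents. The protocol gives a one-sentence list of topics, and the form may ask whether a visit was planned. This is fair: one can say only that no such attribute is stated.
- Eligibility ties enrolled patients to a cardiologist at MGH, and BWH controls to one at BWH. Most cardiology follow-up should then sit in MGB records, where coordinators could classify visits. The Sponsor paragraph of Privacy and Confidentiality also says that the app draws appointment dates and locations from the record. This limits the size of the problem for cardiology visits, but supplies no rule for *unexpected*. It says little about emergency, urgent or primary care elsewhere.
- The outcome is the last of six exploratory ones in a single-arm pilot of about 70 patients. This stands, and it sets the severity.

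A reader might go further and infer that 6a is a single pooled rate, in which a rise in rehab cancels a fall in acute care and makes the outcome uninterpretable. The documents do not support that. Nothing says that the components are added. The text begins in the plural with "Rates ancillary healthcare resources", and the calls list each type separately. Where the protocol does combine activities, as in app usage (outcome 3), it gives the counting rule. Separate reporting is not stated either, so saying so is a useful clarification of wording.

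**Conclusion.** The point holds as under-specification with unequal ascertainment. As described, the ambulatory component can mix planned with unexpected visits, and every component can include outside-MGB events in enrolled patients that are not sought in controls. The first effect pulls the ratio toward 1 when planned visits are similar in the two groups. The second inflates apparent use in the enrolled group.

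The sizes in the working are illustrations that rest on assumed rates, equal planned visits, an equal outside share and complete recall on the calls. They show direction and possible scale, not an expected result.

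It does not follow that unexpected visits can never be identified, since chart review could classify those at MGB. What is missing is a common rule and equal application of it. Severity is low: the outcome is exploratory, and the primary conversion-rate and MAUQ outcomes do not depend on it.

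**What to change.** In outcome 6a:

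1. Base every comparison with controls (emergency visits, urgent care visits, unscheduled ambulatory visits, rehab enrollment) on MGB records only.
2. Define an unscheduled visit by one EHR visit-type rule and apply it identically to enrolled patients and controls. If charts are reviewed to confirm visits, do so in both groups.
3. State that each component is reported as its own rate, with no pooled total, and describe the rehab component as enrollment.
4. Report outside-MGB events from the 30- and 60-day calls descriptively, for enrolled patients only. Add a scheduled/unscheduled item to the calls if those ambulatory visits are to be described as unexpected. That item serves the description and does not enter the comparison with controls.

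The cost is a few sentences of outcome wording, one abstraction rule and, if wanted, one field on the call form, which must be in place before the calls are made. The downside is fewer events, less precise rates, and a comparison that leaves out care received elsewhere. It also assumes that a similar share of each group's care takes place at MGB, which should be stated as a limitation.
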